#### 4.4.2. Co-design workshops

In addition to facilitator notes taken during sessions, transcripts will be reviewed with further note taking to ensure all key decision points and drivers were captured and no key details were missed relevant to intervention development.

## 4.5. Participant discontinuation/withdrawal

Participants will be free to withdraw from the study at any stage without providing a reason.

Participant discontinuation will occur with any of the following:

- Completion of the study protocol
- Illness requiring hospital readmission
- Death of a participant or commencement of end-of-life care
- Loss of capacity to consent to continue participation
- Participant decision to withdraw
- Investigator decision
- Study management group or chief investigator decision

If a patient wishes to withdraw or is discontinued from the study, the following procedures will be observed:

- Withdrawal of consent/ discontinuation of the study will be clearly documented in study documentation and the participant's medical record.
- No further data will be collected from the participant. However, existing data held will be retained and used for the study.

# 5. Data handling

Study data will be securely collected, stored and analysed as described below and in accordance with data protection laws. Informed consent will be obtained to cover this activity. This is described in the study Participant Information Sheet. Participants will also consent to inspection of their data and/or medical records by regulators.

Data will be checked for accuracy, consistency and completeness by manual or electronic checks. Discrepancies in the data will be brought to the attention of the study team as necessary. Resolutions to these issues will be reflected in the dataset.

If the results of the study are published, the subject's identity will remain confidential. The investigator will maintain a list based on screening logs to enable subjects' records to be identified.

## 5.1. Data collection, storage, access and transfer

Participant paper CRFs, completed COM-B questionnaires and workshop facilitator notes will be stored securely in the site files in locked offices on NHS premises. Paper data will converted to a password protected electronic formats (e.g. Microsoft excel/Microsoft word)

Interview and workshop audio recordings will be transferred from their encrypted recorders and stored securely on NHS servers with password protection. Audio files will be converted to a pseudo anonymised password protected transcript file by an approved transcription service for subsequent transfer and analysis. A data management agreement will be in place between the transcription service and sponsor. Once transcribed, original audio files will be deleted.

Direct access to data will be granted to authorised representatives from the Sponsor, academic institutions and the regulatory authorities to permit study-related monitoring, audit and inspections.

Whilst data will be pseudo-anonymised prior to transfer to study team members at partner academic institutions for storage and analysis, specific informed consent will be sought from participants allow

Transfer of pseudo anonymised data will be between secure institutional email accounts e.g. nhs.net to ac.uk.

## 5.2. Confidentiality

All study team members must comply with the requirements of The Data Protection Act 2018 and General Data Protection Regulations 2018 regarding the collection, storage, processing and disclosure of personal information and will uphold the Act's core principles. Any personal data recorded will be regarded as confidential, and any information which

would allow individual participants to be identified will not be released into the public domain.

## 5.3. Archiving

The study data will remain the property of South Tees Hospitals as per the data agreement. A complete copy of the study data will be kept on the trust secure IT service at the end of the study. At the end of the study, all documents and data relating to this project will be stored securely at the trust for 5 years following project completion.

Sites must retain source data and documents associated with this clinical trial until the Sponsor provides written permission to destroy the documents. The Chief Investigator must notify the Sponsor if he/she wishes to assign the essential documents to someone else, remove them to another location or is unable to retain them for a specified period.

## 6. Administrative, Ethical and regulatory compliance

## 6.1. Study Sponsor

South Tees Hospitals NHS Foundation Trust, James Cook University Hospital, [name] will be the study sponsor. Study management responsibilities will be delegated to the chief Investigators and study team.

#### 6.2. Peer review

This project has been peer reviewed as part of a competitive application for funding. In addition, the protocol is planned for submission for publication in a peer-reviewed journal.

## 6.3. Funding body

This study is funded Jointly by Macmillan Cancer Care and Sport England.

## 6.4. Ethical approval

No study activity will be undertaken until ethical approval has been confirmed. The study protocol and associated documentation have undergone assessment by a HRA Ethics Committee (North West- Preston Research Ethics Committee 21/NW/0219). Progression to stage 2 of this study will be by substantial amendment.

## **6.5 Participating sites**

Participating sites have been pre-selected and will confirm capacity and capability prior to commencement. All investigators and key study personnel will have undertaken Good Clinical Practice (GCP) training appropriate to their role.

The study will be conducted in accordance with, but not limited to, ICH/GCP, the Human Rights Act 1998, The Data Protection Act 2018/General Data Protection Regulations 2018, Freedom of Information Act 2000 and the UK Policy framework for Health and Social Care research.

Participants will be informed of how data are recorded, collected, stored and processed, in accordance with The General Data Protection Regulation (GDPR) (EU) 2016/679.

## 6.6. Participant and public involvement

This study protocol and the prototype digital platform are the direct result of a prior body of PPI activity conducted by the study team with patients approaching major surgical intervention and participants in an existing face-to-face prehabilitation service. Patients are central to the stage 1 co-design process and at least one patient representative from the stage 1 participant development group will be invited to sit on the study management group prior to commencement of stage 2.

## 6.7. Study monitoring and interim reporting

A study management group (SMG) will be established by the chief investigators prior to the commencement of stage 2 with representation from the sponsor, participating sites and institutions and research partners. The group will oversee conduct of the feasibility study and meet on a regular basis as required.

remote monitoring of data will be performed. Triggered monitoring, or audit, may be performed if required. Routine monitoring of stage 2 will occur in accordance with the sponsors protocols.

The investigators will permit study related monitoring, audits, HRA/ REC review, providing direct access to all data and documents as required. South Tees Hospitals NHS Foundation Trust has accepted the role of sponsor of the study and will put in place appropriate governance and oversight arrangements

## 6.8. Protocol Compliance

Intentional protocol deviations are not permitted under any circumstances. The study team will record technical/minor deviations. Deviations will include isolated issues that do not put participants at risk of harm nor risk data credibility. The sponsor will be notified of other deviations significantly impacting the risk profile of the study or significantly interrupting study services or supplies. Identified or suspected serious breaches of the study protocol or principles of GCP will be notified to the Sponsor.

#### 6.9. Protocol Amendments

Planned research activity changes will require an amendment initiated by the chief investigators. Proposed changes will be submitted in writing to the sponsor. Amendments will be categorised as substantial or non-substantial.

Required changes in documentation following original ethical approval will also be submitted as an amendment to the Health Research Authority (HRA) by the study team. Substantial amendments will not be implemented until REC and HRA approval are provided if required.

An amendment history log will be maintained by the study team ensuring the most recent versions of the protocol and related documents are in use.

## 6.10. Liability and indemnity

The sponsor is an NHS organisation. The NHS indemnity scheme will apply in the event of harm to participants arising from the study management.

## 6.11. Study summary report

The study team and chief investigator are responsible for compiling and submitting the final study report to the sponsor and REC within one year of study closure.

## 6.12. Early dissemination of important safety findings

Any findings likely to impact patient care in a positive or negative manner will be fed back via research site governance structures

## 6.13. Publication policy

The study data will belong to South Tees Hospitals NHS Foundation Trust as sponsor. The chief investigator will act as the data custodian. The study results will be offered for publication in a peer reviewed journal, on behalf of all collaborators.

Participants will be given the option to request a summary of the study results if requested.

# 7. Adverse event reporting

#### 7.1. Terms and Definitions

#### 7.1.1. Adverse Events

An Adverse Event (AE) is defined as any untoward medical occurrence in a participant who has undergone a research procedure, including occurrences which are not necessarily caused by or related to that procedure.

#### 7.1.2. Serious Adverse Events

A Serious Adverse Event (SAE) is defined as an untoward occurrence that:

- Results in death
- Is life-threatening
- Requires hospitalisation or prolongation of existing hospitalisation
- Results in persistent or significant disability or incapacity
- Consists of a congenital anomaly or birth defect
- Is otherwise considered medically significant by the investigator

#### 7.1.3. Notes on Adverse Event Inclusions and Exclusions

The risk of AEs/SAEs relating to stage 1 of this project is felt to be low. We will ensure clear channels for participants to raise non-emergency concerns with the study team and how to access help.

Common Terminology Criteria for Adverse Events (CTCAE Version 5.0) grading will be used to assess adverse events and adverse device effects.

The safety reporting window includes AEs that occur from the time of participant consent to the end of their involvement in the study. AE and ADEs will be followed up until event resolution (for ADEs) or stabilisation.

Any adverse event included in the criteria outlined above will be documented in the study notes. The AE will be assessed for seriousness, causality and expectedness by a designated clinician.

Any adverse events identified which meet the criteria to be reported as an SAE will be recorded using the sponsor approved SAE form and submitted to the Chief Investigator within 24 hours of the study team becoming aware of the event. Upon receipt, the Chief Investigator will review the event and the following will be considered:

- Whether there is a causal link with study participation.
- Whether the event is, or is not expected.

The outcome of the assessment will be documented and filed in the trial master file and the sponsor informed.

## 7.2. Adverse events of Special Interest

There are no adverse events of special interest.

## 7.3. Reporting of Serious Adverse Events

An SAE occurring to a research participant will be reported to the REC where in the opinion of the Chief Investigator the event was:

- "Related" that is, it resulted from administration of any of the research procedures, and
- "Unexpected" that is, the type of event is not listed in the protocol as an expected occurrence

Related here refers only to SAEs resulting from the application of the biosensor.

Reports of related and unexpected SAEs will be submitted to the REC within 15 days of the Chief Investigator becoming aware of the event, using the 'Non-CTIMP safety report to REC form'. https://www.hra.nhs.uk/approvals-amendments/managing-your-approval/safety-reporting/

A copy of the complete report and the REC acknowledgement will be forwarded to the sponsor.

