## 1.2. Study design:

This protocol details stage 1 of a planned 2 stage process:

**Stage 1:** Systematic development of the digital multibehavioural prehabilitation intervention and healthcare professional (HCP) training resource

**Planned Stage 2:** Feasibility testing of the intervention with patients approaching major surgery at two National Health Service (NHS) centres

The digital multibehavioural intervention will comprise a web-based programme accessible via desktop, tablet and mobile phone. The programme and an accompanying training resource for HCPs will be co-designed with patients and HCPs to facilitate health behaviour changes toward improved preoperative physical and mental health and wellbeing and reduced perioperative risk.

It will provide structured support to facilitate simultaneous multibehavioural change. The intervention will include a number of components designed to run over the 4-8 weeks prior to surgery. These may inlcude:

- Structured exercise (aerobic, resistance and inspiratory muscle training)
- Smoking cessation
- Reduction of alcohol intake
- Improved nutrition
- Engagement in self-management behaviours to improve psychological health and wellbeing (reduction of stress, anxiety and depression)
- Sleep duration and quality

Ethical approval to commence stage 2 will be sought via substantial amendment pending progress through stage 1

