## 4.2. Stage 1 recruitment and consent

#### 4.2.1. Patient participants

A list of potential patient participants approaching or having undergone major non-cardiac surgery will be identified by screening of surgical and anaesthetic preassessment clinic lists and electronic health records alongside communication with Macmillan cancer care coordinators. A stage 1 patient participant information sheet (PIS) will be sent by post inviting the patient to join a co-design group. Potential participants will be able to contact the study team directly by telephone or email to express an interest in taking part. Potential participants who do not contact the team will receive a follow-up telephone call 7 days following postage of the PIS to confirm receipt and enquire as to whether they are interested in taking part to allow completion of the screening log.

Those wishing to join the group as participants will complete the stage 1 patient participant consent form prior to any data collection.

Patient participants will be recruited from both hospital sites. The total number of participants will be guided by the developmental process and participants may wish to contribute to all 3 aspects of stage 1 data collection (self-evaluation questionnaire; semi-structured interview and co-design workshops):

- 10 patient participants will initially be invited to complete a COM-B self-evaluation questionnaire, increasing up to 20 participants guided by interim analysis.
- 10 patient participants will initially be invited to undertake a semi-structured, interview, increasing up to 20 participants guided by interim analysis.
- 10-15 patient participants will be invited to contribute to co-design workshops.

We will ask participants to undertake either:

- 1. Completion of the COM-B questionnaire and a semi-structured interview.
- 2. Questionnaire, interview and to participate in the co-design workshop series.

We also anticipate that participants may wish to bring a partner, family member or one other person with them to attend co-design workshop sessions or contribute to interviews. We would welcome their contributions to the co-design process, and we will ask individuals attending in support of patients to also complete the stage 1 patient participant consent form in order that their contribution to workshops can be recorded, analysed and used to inform intervention development.

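### Section 7.3 limits REC-reportable SAEs to those caused by a biosensor the study does not describe, contradicting its own definition of related and the causality test in 7.1.3

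*Protocol*

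**What the plan says.** Section 7.3 sets two conditions for reporting an SAE to the REC, both judged by the Chief Investigator. The event must be related, meaning that "it resulted from administration of any of the research procedures", and it must be unexpected, meaning that its type is not among the expected occurrences listed in the protocol. Directly after these two conditions comes the sentence "Related here refers only to SAEs resulting from the application of the biosensor". The time limit follows: "Reports of related and unexpected SAEs will be submitted to the REC within 15 days", counted from when the Chief Investigator becomes aware of the event.

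Section 7.1.3 covers the steps before that. A designated clinician assesses each adverse event for seriousness, causality and expectedness. An SAE goes to the Chief Investigator within 24 hours of the study team learning of it. The Chief Investigator then considers "Whether there is a causal link with study participation" and whether the event was expected. The outcome is filed and the sponsor is told. The same section says that CTCAE "grading will be used to assess adverse events and adverse device effects".

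On scope, section 1.2 states: "This protocol details stage 1 of a planned 2 stage process". Section 4.2.1 refers to "all 3 aspects of stage 1 data collection (self-evaluation questionnaire; semi-structured interview and co-design workshops"). Section 1.2 describes the product being developed: "The digital multibehavioural intervention will comprise a web-based programme accessible via desktop, tablet and mobile phone".

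**The concern.** The words *here* and *only* make the biosensor sentence an express limit on the definition just above it, not an example of it. If the limit is applied in a study that uses no biosensor, nothing can be related for the purpose of section 7.3, and the REC report cannot be triggered.

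The question could arise in practice. Under section 4.1.1, patient participants are preparing for major surgery or are within 3 months of it, and section 2 cites postoperative complication rates of 15-40%. SAEs that need a relatedness decision are therefore foreseeable, even if few or none are caused by the study. Section 4.3.3 acknowledges a continuing Covid-19 risk and offers face-to-face attendance at up to 6 workshops of up to 2 hours each. An admission to hospital for an infection caught at a workshop would be an SAE arising from a research procedure, and the literal rule would keep it from the REC. What is at stake is the study's external safety report. No estimate or analysis is affected.

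**Working it through.** No arithmetic applies. The check sets the relevant statements side by side.

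**Step 1: is there a biosensor in the study?** The places where one would be described are:

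- Section 1.2: a web-based programme used on a desktop, tablet or phone. No biosensor.
- Section 1.3, stage 2 outline: baseline assessment, access to the intervention, and reassessment before surgery and 3 months after it. No biosensor.
- Section 4.3 with 4.3.1 to 4.3.3: CRF data, COM-B questionnaires, interviews and workshops. No biosensor.

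The sentence in 7.3 is the only mention of a biosensor in the text available for review. The opening pages of the protocol were not part of that text, but all the sections that describe procedures were.

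**Step 2: how many tests of relatedness are there?**

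| Place | Test | Use |
|---|---|---|
| 7.1.3 | causal link with taking part in the study | Chief Investigator's review, filed and sponsor informed |
| 7.3, first condition | resulted from any research procedure | REC report |
| 7.3, later sentence | resulted from applying the biosensor only | REC report |

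The second and third tests serve the same purpose and exclude each other. The third also conflicts with the first: an SAE can be judged causally linked under 7.1.3 and still not be related under 7.3.

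**Step 3: what follows from each reading of 7.3?** An SAE is reportable if it is related AND unexpected.

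- *Expectedness.* The text available lists no expected events, and section 7.2 names no events of special interest. Every SAE is therefore unexpected on the 7.3 test, and relatedness alone decides.
- *Narrow reading.* Related requires the application of a biosensor. None is applied, so no SAE is related and none is reportable.
- *Broad reading.* Related requires a research procedure. An SAE caused by a questionnaire, interview or workshop is related and reportable within 15 days.

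**Step 4: which safety steps depend on the biosensor sentence?** Only the REC report in 7.3. Recording, clinician assessment, the 24-hour report to the Chief Investigator, the causality review and informing the sponsor all sit in 7.1.3, which has no biosensor limit.

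**The case against.** The best reply is that the sentence does little harm. The broader definition stands in the same section, the decision rests on the Chief Investigator's opinion, and someone who finds no biosensor in the study may simply apply the broader definition. Section 7.1.3 describes the stage 1 risk as low. Stage 2, in which patients would use the programme, needs a substantial amendment (sections 1.2 and 6.4), so the safety section can be revised before then. No stage 1 outcome in section 1.7 depends on this wording.

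Most of this is fair, and it limits how much weight the point can bear. It does not rescue the sentence, which is wrong for this study on any reading. Section 6.8 rules out intentional deviations, so staff should not have to disregard a written limit in order to report properly.

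Three stronger readings are tempting, and the protocol does not support them:

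- *A procedure-caused SAE would be recorded as unrelated.* It would not. Causality is assessed under 7.1.3 without a device limit, and the biosensor sentence governs only 7.3.
- *A finding of no related SAEs would be guaranteed by definition.* The outcomes (1.7) and objectives (3) contain no safety conclusion, and the causality record under 7.1.3 would be available if one were drawn.
- *No SAE could receive any prompt report.* The 24-hour report to the Chief Investigator is untouched.

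The device wording in 7.1.3 suggests that text was carried over from another protocol. That is an inference. The contradiction does not depend on it.

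**Conclusion.** The point holds as an internal contradiction. Section 7.3 gives two incompatible definitions of a related SAE for REC reporting, and the narrower one also conflicts with the causality test in 7.1.3. If the narrower definition is followed, no SAE caused by a stage 1 procedure meets the 15-day REC rule. If the broader one is followed, the rule works. Nothing in the protocol says which prevails, although the wording of the later sentence favours the narrow reading.

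The effect is limited to the REC report. This rests on two assumptions: that the pages not available for review do not introduce a biosensor, and that the later sentence is read as the limit it states. Stage 1 risk is low by the protocol's own account. Even so, this is an operative safety rule that gives the wrong result when followed as written, and it should be corrected.

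**What to change.** Delete the biosensor sentence from section 7.3. The definition already there, covering any research procedure, then governs REC reporting. It should not be replaced by a list of named procedures: a list of questionnaire, interview and workshop, for example, would leave out CRF collection and be narrower than the present wording.

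Reconcile that definition with the test in 7.1.3, which refers to study participation. The two are close but not identical: an event on the way to a workshop might be linked to participation without resulting from a procedure. State how the Chief Investigator's causality decision under 7.1.3 feeds the REC decision under 7.3, so that one assessment serves both.

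Removing or explaining the adverse-device-effect wording in 7.1.3 is optional tidying. It does not change which SAEs reach the REC.

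The cost is a few lines in two subsections, submitted as a protocol amendment under section 6.9. Recruitment, sample size, data collection and analysis are unaffected.
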